6.7. Common Calculations

For quantitative measurements, change from baseline will be calculated as:

- Test Value at Visit X – Baseline Value

6.8. Software Version

[figure not shown]
Non-compartmental PK parameter calculations will be performed using Phoenix® WinNonlin® 8.3 or higher (Certara, Princeton, New Jersey) or SAS Version 9.4 or higher (SAS Institute, Inc., Cary, North Carolina). All other derivations, summaries, and listings will be generated using the same version of SAS. Graphics will be prepared using the same version of SAS.

7. STATISTICAL CONSIDERATIONS

7.1. Missing Data

Missing safety data will not be imputed.

Missing PK data will be handled as described in Section 15 of this analysis plan.

8. OUTPUT PRESENTATIONS

Appendix 1 shows conventions for presentation of data in outputs.

The output shells provided with this SAP describe the presentations for this study and therefore the format and content of the summary tables, figures, and listings to be provided by IQVIA Biostatistics.

Some minor modifications may be necessary to the planned design of tables, figures, and listings to accommodate data collected during the actual study conduct.

9. DISPOSITION AND WITHDRAWALS

[figure not shown]
All participants who provide informed consent will be accounted for in this study. Participant disposition will be tabulated for each study treatment and for all participants combined with the number of participants who are randomly assigned to treatment, dosed, complete the study, prematurely discontinue, and the reason for early discontinuation. A listing will present dates of completion or early withdrawal and the reason for early discontinuation, if applicable, for each participant.

Listings of study eligibility with inclusion/exclusion criteria responses, treatment randomization, and study treatment administration will be provided.

10. DEMOGRAPHIC AND OTHER BASELINE CHARACTERISTICS

Demographic characteristics such as age, sex, race, ethnicity, height, weight (assessed at Screening), and body mass index (BMI) will be summarized and tabulated by treatment and for all subjects overall. Descriptive statistics will be presented for age, height, weight, and BMI. Frequency counts and percentages will be presented for sex, race, and ethnicity. No statistical testing will be carried out for demographic or other baseline characteristics.

Individual subject demographics and results from viral serology, drug of abuse/alcohol screening, COVID-19 testing, pregnancy tests, and follicle-stimulating hormone (FSH) test will be presented in listings.

11. PROTOCOL DEVIATIONS

11.1. Deviations Related to Study Conduct

A deviation from a protocol occurs when Investigator site staff or a study participant does not adhere to the protocol's stipulated requirements, whether inadvertently or planned. Protocol deviations will be listed and will include a classification of minor or major, as determined by clinical staff.

11.2. Deviations Related to PK Analysis

Changes to the procedures or events, which may impact the quality of the PK data, will be considered important protocol deviations and will be described within the clinical study report body text. These changes or events will include any circumstances that will alter the evaluation of the PK. Examples include, but may not be limited to, sample processing errors that lead to inaccurate bioanalytical results, and/or inaccurate dosing on the day of PK sampling. In the case of an important protocol deviation or event, PK data collected during the affected treatment period will be excluded from the study results. Other changes to the procedures or events which do not impact the quality of the PK data will not be considered important protocol deviations. A common example of a non-significant protocol deviation is a missed blood sample or deviations from blood collection times.

[figure not shown]

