Abbreviations: AE = adverse event; A_e = amount; AUC = area under the concentration versus time curve; AUC_(0-inf) = AUC from time zero extrapolated to infinity; AUC_(0-last) = AUC from time zero to the last quantifiable concentration; C_{EOI} = concentration at the end of 10-minute IV infusion; CL = systematic clearance; CL_r = renal clearance; C_{max} = maximum concentration; ECG = electrocardiogram; f_e = fraction; IV = intravenous; λ_z = elimination rate constant; PK = pharmacokinetics; t_{1/2} = half-life; QTcF = QT corrected for heart rate by Fridericia's formula; t_{max} = time to C_{max}; V_{ss} = volume of distribution at steady-state following intravenous dosing; V_z = volume of distribution following intravenous dosing.

Overall Design:

CS-1103-01 is a Phase 1a, single center, double-blind, placebo-controlled, randomized, single ascending-dose first in-human (FIH) study. All participants will be screened within 28 days of dose administration and participants will check-in to the inpatient clinical research unit (CRU) on their Admission/Day -1. Participants will be randomized on Day -1, the day prior to dosing, after meeting all eligibility criteria. Participants are scheduled to remain in the CRU for up to 48 hours postdose for safety and PK assessments.

Number of Participants:

Up to 40 healthy participants, aged 18 to 55 years will be randomized.

Intervention Cohorts and Duration:

Up to 5 cohorts of 8 participants (6 active, 2 placebo participants per cohort) will be enrolled with each participant assigned to receive a single dose of CS-1103 or placebo on 1 occasion (Day 1). Note: The dose will be capped at 3000 mg.

- Cohort 1: Dose level 1 (CS-1103 2.7 mg/kg, [REDACTED] or placebo [REDACTED])
- Cohort 2: Dose level 2 (CS-1103 8.0 mg/kg, [REDACTED] or placebo [REDACTED])
- Cohort 3: Dose level 3 (CS-1103 16.0 mg/kg, [REDACTED] or placebo [REDACTED])
- Cohort 4: Dose level 4 (CS-1103 26.7 mg/kg, [REDACTED] or placebo [REDACTED])
- Cohort 5: Dose level 5 (CS-1103 40.0 mg/kg, [REDACTED] or placebo [REDACTED])

The study duration will be approximately 37 days.

- Screening Period: up to 28 days
- CRU confinement period: 4 days
 - Treatment administration: 1 day
- CRU discharge through follow-up/end of study period: 5 days

Statistical Methods:

Descriptive statistics will be used as applicable to summarize the study data unless otherwise specified. Continuous variables: Sample size (n), mean, standard deviation (SD), median,

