3.0 OBJECTIVES AND ENDPOINTS

Objectives	Endpoints
Primary 
 To assess the safety and tolerability of CS-1103, administered by IV infusion 	Standard safety and tolerability parameters but not limited to: 
 AE Vital signs (blood pressure, pulse rate, respiratory rate, oxygen saturation, and body temperature) Digital 12-lead ECGs/Holter Laboratory parameters (clinical chemistry, hematology, coagulation, urinalysis)
Secondary 
 To characterize the PK of CS-1103, administered by IV infusion 	Plasma and urine PK parameters including but not limited to 
 C_{max}, t_{max}, C_{EOI}, $AUC_{(0-last)}$, $AUC_{(0-inf)}$, $t_{1/2}$, λ_z, CL, V_{ss}, and V_z By-interval and cumulative CS-1103 excretion in urine (A_e and f_e) CL_r
Exploratory 
 To explore the relationship between CS-1103 plasma concentrations and changes in QT intervals during dosing, if any 	
 Concentration-QT correlation performed on baseline-corrected QTcF time-matched with PK. Concentration-QT correlation may be reported separately from the clinical study report

Abbreviations: AE = adverse event; A_e = amount; AUC = area under the concentration versus time curve; $AUC_{(0-inf)}$ = AUC from time zero extrapolated to infinity; $AUC_{(0-last)}$ = AUC from time zero to the last quantifiable concentration; C_{EOI} = concentration at the end of 10-minute IV infusion; CL = systematic clearance; CL_r = renal clearance; C_{max} = maximum concentration; ECG = electrocardiogram; F_e = fraction; IV = intravenous; λ_z = elimination rate constant; PK = pharmacokinetics; $t_{1/2}$ = half-life; QTcF = QT corrected for heart rate by Fridericia's formula; t_{max} = time to C_{max} ; V_{ss} = volume of distribution at steady-state following intravenous dosing; V_z = volume of distribution following intravenous dosing.

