9.2 Analysis Sets

For the purposes of analysis, the following analysis sets are defined:

- Safety Analysis Set: All participants who have received one dose of study treatment (CS-1103 or placebo)
- Pharmacokinetic Analysis Set: All participants who have received one dose of CS-1103 and have at least 1 quantifiable plasma or urine postdose concentration, without protocol deviations or events expected to affect PK results

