5.3. Pharmacokinetic Analysis Set

The pharmacokinetic analysis set will consist of all participants who receive active study treatment (CS-1103) and

have at least 1 measured plasma or urine concentration at a scheduled PK time after start of dosing for at least 1 PK analyte without protocol deviations or events with potential to affect the pharmacokinetic concentrations. Participants in this population will be used for all PK analyses.

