15. PHARMACOKINETIC ANALYSIS

15.1. Plasma Concentration Data

Participants with partial data will be evaluated on a case-by-case basis to determine if sufficient data are available for reliable estimation of PK parameters.

[figure not shown]
A listing of PK blood sample collection times as well as derived sampling time deviations will be provided.

Plasma concentrations will be summarized using descriptive statistics for each active treatment using the PK Analysis Set. Concentrations that are below the limit of quantitation (BLQ) will be treated as zero for the computation of descriptive statistics.

A subject listing of all concentration-time data for each treatment will be presented. Figures of arithmetic mean concentration-time data (\pm SD, as appropriate) will be presented for each treatment on linear and semi-logarithmic scales. Individual subject concentration-time data will be graphically presented on linear and semi-logarithmic scales.

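### SAP 11.2, read literally, removes a participant's whole PK profile for one inaccurate concentration, while a missed sample costs one point

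*SAP*

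**What the plan says.** PK is the trial's secondary objective (protocol 3.0: "To characterize the PK of CS-1103, administered by IV infusion"). Each dose level has 6 active participants, and each participant receives one infusion on one day.

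SAP 11.2 calls changes or events that may impair the quality of the PK data important deviations. Its examples are inaccurate dosing and "sample processing errors that lead to inaccurate bioanalytical results". For an important deviation, "PK data collected during the affected treatment period will be excluded from the study results". The section sets no minimum number of affected samples and offers no option to drop a single result. The same paragraph then says: "A common example of a non-significant protocol deviation is a missed blood sample or deviations from blood collection times".

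Three other places bear on this:

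- SAP 5.3 defines the PK Analysis Set with the condition "without protocol deviations or events with potential to affect the pharmacokinetic concentrations", and uses that set for all PK analyses. Protocol 9.2 has a narrower trigger: "without protocol deviations or events expected to affect PK results".
- SAP 15.1 says: "Participants with partial data will be evaluated on a case-by-case basis". The question there is whether enough data remain for reliable parameters.
- SAP 15.2 already works at sample level. A below-quantitation value lying between two quantifiable ones after Cmax is treated as missing, and the rest of the profile is kept.

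**The concern.** Two events that leave the analyst with the same information are handled very differently. A tube that was never drawn and a tube whose result is known to be wrong both leave one time point without a usable value. Under SAP 11.2 the first costs that point. The second, on the literal wording, costs every plasma point and, since the sentence covers PK data without distinction, the urine data as well.

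The phrase about the treatment period would limit the loss in a crossover trial, where a participant has other periods. In a single-dose trial there is only one period, so it limits nothing. What is at stake is precision in cohorts of 6: the PK summaries at that dose and that participant's contribution to the dose-proportionality model.

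**Working it through.** The documents state no power calculation or expected loss for PK, so there is no figure of the plan's to reproduce. The check has four steps.

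**1. Inputs from the documents.** There are 6 active participants per dose and 30 over five cohorts (protocol 4.1). The detailed schedule in protocol 1.3 has 19 plasma samples per participant: predose, end of infusion (EOI), 5, 10, 20, 30 and 40 minutes, and 1, 1.5, 2, 2.5, 3, 4, 6, 8, 12, 24, 36 and 48 hours. At least 3 quantifiable postdose concentrations are needed for PK parameters, and at least 3 values per dose for the power model (both SAP 15.2).

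**2. Cost of one excluded profile.** The half-width of a 95% t-interval is t(0.975, n−1) × SD / √n.

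- n = 6: 2.571 / √6 = 1.049 SD
- n = 5: 2.776 / √5 = 1.242 SD
- Ratio: 1.242 / 1.049 = 1.18, so about 18% wider at equal SD

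One profile is 1/6 = 16.7% of the active data at that dose. One postdose sample is 1/18 = 5.6% of one participant's postdose plasma points.

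**3. How often it might happen.** The per-sample rate p is an assumption. It means an error that gives an inaccurate result, is recognised, and is not recovered. With independent errors, the chance of losing a profile is q = 1 − (1 − p)^19. The chance that a cohort keeps fewer than 3 of 6 is P(X ≥ 4) for X binomial(6, q).

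| Assumed p | Profiles lost, q | Expected of 30 | A given cohort below 3 | Any of 5 cohorts below 3 |
|---|---|---|---|---|
| 0.1% | 1.9% | 0.6 | <0.001% | <0.001% |
| 0.5% | 9.1% | 2.7 | 0.09% | 0.4% |
| 1% | 17.4% | 5.2 | 1.0% | 5.0% |
| 2% | 31.9% | 9.6 | 8.6% | 36% |

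Counting only the 18 postdose samples changes little: at 1%, q is 16.5% and 5.0 of 30 profiles go.

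**4. Cost of dropping one sample instead.** The illustration uses the protocol 4.5 prediction at 40.0 mg/kg (C0 340 µg/mL, AUC(0-last) 318 µg·hr/mL). One-phase and two-phase decline and quantitation limits of 0.01 to 1 µg/mL are assumed. Each scheduled sample was left out in turn, with linear-up/log-down AUC and time counted from the start of infusion.

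- Any sample except EOI: AUC(0-inf) changes by at most 0.4%, AUC(0-last) by at most 2.5%, half-life by at most 2.8%, and Cmax not at all. Between 11 and 15 quantifiable points remain, against the required 3.
- The EOI sample: AUC falls by about 5%, observed Cmax falls by about 9% to 11%, and C_EOI is lost.

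So for an isolated bad result other than EOI, almost all the information in the profile survives.

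**The case against.** The strongest reply is that the trigger is narrow. SAP 11.2 concerns errors that make results inaccurate and circumstances that alter the PK evaluation, and it exempts events that leave data quality intact. A reader might infer that any handling slip removes a participant; the text does not say that. A pharmacokineticist might also judge that one bad tube in a full profile does not alter the evaluation. That is sensible, but the section lists such errors as its own example and makes exclusion mandatory, so keeping the profile would depart from the written rule.

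Other parts of the plan soften the effect. Protocol 8.4.1 splits each plasma sample into primary and back-up aliquots, which helps when the error is confined to one aliquot but not when it came before the split. Under protocol 8.4.2 only samples still within known stability on receipt are analysed, so one already out of stability gives no result rather than a wrong one. SAP 15.1 asks whether partial data are sufficient and does not restore data that 11.2 excludes.

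Three stronger readings are tempting and are not supported:

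- **That SAP 5.3 plainly repeats the exclusion.** With no comma before the condition, it can be read as requiring one unaffected concentration, which a single bad tube would not defeat. Protocol 9.2, with its comma, applies the condition to the participant.
- **That the exclusions bias the results.** Nothing in the documents links tube handling to a participant's PK.
- **That dose proportionality is in jeopardy.** At an assumed 1%, the chance that some dose level loses two or more of six is 81%, but the documents set no threshold there. Their threshold is 3 values, for which the chance is about 1% per cohort.

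**Conclusion.** The point stands as a defect in the exclusion rule with a modest, uncertain cost. The literal consequence, 1 of 6 active profiles for one inaccurate concentration, follows from the text alone. The 18% widening needs only equal SD.

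The frequency does not follow from the text. The range of about 2% to 32% of profiles depends on assumed error rates of 0.1% to 2% and on independence. Errors in shared handling steps would cluster, so fewer participants would be affected for the same number of bad samples. When many samples in one profile are hit, excluding all of it is also easier to defend. Back-up aliquots lower the figures further.

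The trial is descriptive, tests no hypotheses, and does not base its sample size on power, so its conclusions are not threatened. The argument for change is that valid data in small cohorts can be kept at almost no cost. It does not extend to inaccurate dosing, where excluding the whole profile is reasonable.

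**What to change.** - **SAP 11.2:** for sample-level errors, set only the affected concentration(s) to missing, flag them in the listings, and derive parameters from the remaining samples under SAP 15.1 and 15.2 (minimum points, adjusted R-squared and 30% extrapolation limits).
- **EOI sample affected:** do not report Cmax or C_EOI for that participant. The drop of about 5% in the illustration is a reason to flag AUC as well.
- **Whole-profile exclusion:** keep it for deviations that affect the dose or infusion, or that leave too few samples.
- **SAP 5.3:** align its trigger with the narrower one in protocol 9.2, and state whether the condition applies to the participant or to the concentration.
- **SAP 3.3:** record the change, since the protocol synopsis and protocol 9.2 exclude at participant level.

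The cost is a few sentences in the SAP and a documented sample-level judgement by the pharmacokineticist whenever a result is set to missing. No change to study conduct or data collection is needed.

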12. SURGICAL AND MEDICAL HISTORY

Medical History coded using Medical Dictionary for Regulatory Activities (MedDRA), the latest version, will be listed for the safety analysis set.

13. MEDICATIONS

Medication usage, coded using the World Health Organization (WHO) Drug Dictionary, the latest version, will be categorized as Prior or Concomitant and listed for the safety analysis set:

- 'Prior' medications are medications which started and stopped prior to the administration of study medication.
- 'Concomitant' medications are medications which were taken during the treatment period, or specifically:
 - started on or after the administration of study treatment

- started prior to the administration of study medication and were continued after the administration of study treatment

See Appendix 2 for handling of partial dates for medications, in the case where it is not possible to define a medication as prior or concomitant, the medication will be classified as concomitant.

14. STUDY MEDICATION EXPOSURE

Study treatment administration will be listed.

15. PHARMACOKINETIC ANALYSIS

15.1. Plasma Concentration Data

Participants with partial data will be evaluated on a case-by-case basis to determine if sufficient data are available for reliable estimation of PK parameters.

[figure not shown]
A listing of PK blood sample collection times as well as derived sampling time deviations will be provided.

Plasma concentrations will be summarized using descriptive statistics for each active treatment using the PK Analysis Set. Concentrations that are below the limit of quantitation (BLQ) will be treated as zero for the computation of descriptive statistics.

A subject listing of all concentration-time data for each treatment will be presented. Figures of arithmetic mean concentration-time data (\pm SD, as appropriate) will be presented for each treatment on linear and semi-logarithmic scales. Individual subject concentration-time data will be graphically presented on linear and semi-logarithmic scales.

15.2. Pharmacokinetic Parameters

For PK parameter calculations, predose samples that are BLQ or missing will be assigned a numerical value of zero. Any anomalous concentration values observed at predose will be identified in the study report and used for the computation of PK parameters. Pharmacokinetic parameters will be computed if the anomalous concentration is not greater than 5% of the observed maximum concentration (C_{max}). If the anomalous concentration is greater than 5%

of C_{max} , the PK parameters for the given subject will be calculated and reported in the listing, but excluded from statistical summaries and analyses.

Any other BLQ concentrations will be assigned a value of zero if they precede quantifiable samples in the initial portion of the profile. A BLQ value that occurs between quantifiable data points, especially prior to C_{max} , will be evaluated to determine if an assigned concentration of zero makes sense, or if exclusion of the data is warranted. Following C_{max} , BLQ values embedded between 2 quantifiable data points will be treated as missing when calculating PK parameters. If a BLQ value occurs at the end of the collection interval (after the last quantifiable concentration), it will be set to zero. If consecutive BLQ concentrations are followed by quantifiable concentrations in the terminal portion of the concentration curve, these quantified values will be excluded from the PK analysis by setting them to missing, unless otherwise warranted by the concentration-time profile.

The following plasma PK parameters will be estimated for CS-1103 by non-compartmental methods using actual elapsed time from the end of infusion. A minimum of 3 quantifiable postdose concentrations will be required for calculation of PK parameters.

C_{max} Maximum concentration, obtained directly from the observed concentration versus time data

C_{EOI} Concentration at the end of the 10-minute IV infusion

t_{max} Time to C_{max}

[figure not shown]
$AUC_{(0-inf)}$ Area under the plasma concentration-time curve from time zero (end of the 10-minute IV infusion) extrapolated to infinity, calculated by linear up/log down trapezoidal summation

$AUC_{(0-last)}$ Area under the plasma concentration-time curve from time zero to the time of the last quantifiable concentration, calculated by linear up/log down trapezoidal summation

CL Systemic clearance, calculated as dose divided by $AUC_{(0-inf)}$

V_z Volume of distribution following intravenous dosing (L), calculated as dose divided by $[\lambda_z \cdot AUC_{(0-inf)}]$

V_{ss} Volume of distribution at steady state following intravenous dosing (L), calculated as mean residence time (MRT) extrapolated to infinity multiplied by clearance

(MRT_{inf}*CL)

t_{1/2} Apparent terminal half-life (h), determined as ln2/λ_z.

λ_z Apparent terminal rate constant (1/h), determined by linear regression of the terminal points of the log-linear concentration-time curve. A minimum of 3 data points will be used for determination.

Dose normalized C_{max}, AUC_(0-inf), and AUC_(0-last) will also be determined. Additional plasma parameters may be calculated if deemed appropriate.

The following PK parameters will be calculated for diagnostic purposes and listed, but will not be summarized.

t_{1/2}, Interval The time interval (h) of the log-linear regression to determine λ_z.

t_{1/2}, N Number of data points included in the log-linear regression analysis to determine λ_z. A minimum of 3 data points will be used for determination.

[figure not shown]
Rsq adj Goodness of fit statistic for calculation of λ_z (Regression coefficient). If the Rsq_adj is less than 0.800, then λ_z and associated parameters (AUC_(0-inf), t1/2, CL, and Vz (Vss)) will be listed but not included in summary and inferential statistics.

%AUC_{ex} Percentage of AUC_(0-inf) obtained by extrapolation, calculated as [(C_{last}/λ_z)/AUC_(0-inf)×100]. If the %AUC_{ex} is greater than 30% of AUC_(0-inf), then AUC_(0-inf), CL, V_z, and V_{ss} will be listed but not included in summary and inferential statistics.

Pharmacokinetic parameters will be summarized by treatment using descriptive statistics. Geometric mean will not be calculated for t_{max}. A subject listing of individual PK parameters for each treatment will be provided.

Scatter plots of individual values and geometric means of PK parameters, AUC_(0-inf) (or AUC_(0-last), if AUC_(0-inf) is not calculable in most participants (75% or more per dose level)), C_{max} (and C_{EOI}, if appropriate) as well as dose-normalized exposure parameters versus dose will be presented.

The dose proportionality of the primary PK parameters, AUC_(0-inf) (or AUC_(0-last), if AUC_(0-inf) is not calculable in most participants (75% or more per dose level)) and C_{max}, over the administered dose range will be investigated using the following power model:

$\log(\text{PK parameter}) = a + b * \log(\text{dose})$
where 'a' is the intercept and 'b' is the slope.

The power model parameters will be estimated using least-squares (LS) regression or an equivalent method. A minimum of 3 values per dose must be available for a given parameter to estimate dose proportionality with the power model. Dose proportionality analysis will not be performed for the secondary PK parameters.

[figure not shown]

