3.1. General Description

CS-1103-01 is a Phase 1a, single center, double-blind, placebo-controlled, randomized, single ascending-dose first in-human (FIH) study. All participants will be screened within 28 days of dose administration and participants will check-in to the inpatient clinical research unit (CRU) on their Admission/Day -1. Participants will be randomized on Day -1, the day prior to dosing, after meeting all eligibility criteria. Participants are scheduled to remain in the CRU for up to 48 hours postdose for safety and PK assessments.

Up to 40 healthy participants, aged 18 to 55 years will be randomized.

Up to 5 cohorts of 8 participants (6 active, 2 placebo participants per cohort) will be enrolled with each participant assigned to receive a single dose of CS 1103 or placebo on 1 occasion (Day 1). Note: The dose will be capped at 3000 mg.

- Cohort 1: Dose level 1 (CS-1103 2.7 mg/kg, [REDACTED] or placebo [REDACTED])
- Cohort 2: Dose level 2 (CS-1103 8.0 mg/kg, [REDACTED] or placebo [REDACTED])

[figure not shown]

- Cohort 3: Dose level 3 (CS-1103 16.0 mg/kg, [REDACTED]) or placebo ([REDACTED])
- Cohort 4: Dose level 4 (CS-1103 26.7 mg/kg, [REDACTED]) or placebo ([REDACTED])
- Cohort 5: Dose level 5 (CS-1103 40.0 mg/kg, [REDACTED]) or placebo ([REDACTED])

Each cohort duration will be approximately 37 days.

- Screening Period: up to 28 days
- CRU confinement period: 4 days
- Treatment administration: 1 day
- CRU discharge through follow-up/end of study period: 5 days

Table A: Study Schema

Abbreviations: CRU = clinical research unit; EOS = end of study, IV = intravenous.

Note: Admission/Day -1 may span 2 days in the CRU, in that case screening will end on Day -3 for participants with Admission Day spanning 2 days in the CRU.

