15.3. Analysis of Urine PK Data

A listing of individual PK urine sample collection start and stop dates/times as well as urine volumes will be provided for each urine collection. Amounts of urine excreted over each planned collection interval for each treatment will be summarized using descriptive statistics for the PK Analysis Set.

The following parameters will be calculated from the urine data:

$A_{e(t1-t2)}$	By-interval amount excreted in urine during the pooled collection interval from t1 to t2 over the following intervals: 0-2 hr, 2-4 hr, 4-6 hr, 6-12 hr, 12-24 hr, 24-36 hr and 36-48 hr
$A_{e(0-\text{last})}$	Cumulative amount excreted in urine during the pooled collection intervals
$f_{e(t1-t2)}$	By-interval fraction of dose (reported as percent) excreted in urine during the pooled collection interval from t1 to t2
$f_{e(0-\text{last})}$	Cumulative fraction of dose (reported as percent) excreted in urine during the pooled collection intervals
CL_r	Renal clearance (L/h), calculated as $A_{e(0-\text{last}2)}$ divided by $AUC_{(0-\text{last})}$.

Urine PK parameters will be summarized by treatment using descriptive statistics for the PK Analysis Set. A participant listing of individual urine PK parameters for each treatment will be provided. Geometric mean and individual cumulative percent CS-1103 excreted in urine versus time curves by dose will also be presented on linear scale.

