APPENDIX 1. PROGRAMMING CONVENTIONS FOR OUTPUTS

IQVIA Output Conventions

Outputs will be presented according to the IQVIA Global Biostatistics Standard Output Conventions, which is available upon request.

Dates & Times

Depending on data availability, if not otherwise specified, dates will take the format DDMMMYYYY; times will take the format hh:mm; combined dates and time will take the format DDMMMYYYY/hh:mm.

Spelling Format

English US.

Presentation of Treatment Groups

For outputs, treatment groups will be represented as follows, as appropriate:
Placebo, CS-1103 xx mg/kg, All Active (when applicable), All Subjects.

[figure not shown]
Presentation of Visits

For outputs, visits will be represented as collected on eCRF, as appropriate.

Listings

All listings will be ordered by the following (unless otherwise indicated in the template):

- Cohort/Treatment (cohort only presented when applicable)
- Subject number
- Date and Time (where applicable) of assessment
- For listings where non-randomized subjects are included (if applicable), these will appear in a category after the randomized treatment groups labeled 'Not Randomized'

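### Does leaving dose undefined in the power model let the 3000 mg cap bias the dose-proportionality result at 40 mg/kg?

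*SAP*

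**What the plan says.** SAP 15.2 fits log(PK parameter) = a + b·log(dose) to AUC(0-inf) (or AUC(0-last)) and Cmax, and states that proportionality "over the administered dose range will be investigated using the following power model". Dose-normalised Cmax and AUC are also derived; individual values and geometric means are plotted, and these "as well as dose-normalized exposure parameters versus dose will be presented". The data requirement is worded by level: "A minimum of 3 values per dose must be available for a given parameter to estimate dose proportionality with the power model". SAP Appendix 1 labels the groups "Placebo, CS-1103 xx mg/kg, All Active (when applicable), All Subjects".

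Elsewhere in the same section, CL is "Systemic clearance, calculated as dose divided by" AUC(0-inf), and V_z is "Volume of distribution following intravenous dosing (L), calculated as dose divided by" the product of λ_z and AUC(0-inf). SAP 15.3 reports urinary recovery as "Cumulative fraction of dose (reported as percent) excreted in urine during the pooled collection intervals".

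The cap appears in SAP 3.1: "The dose will be capped at 3000 mg". It is also in the protocol synopsis and Protocol 4.1. The visible analysis sections do not mention it.

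**The concern.** Nominal and actual dose normally coincide in a weight-based single-dose study, so nobody needs to say which is meant. Here the cap separates them at the top level. A participant above 75 kg assigned to 40 mg/kg receives 3000 mg, which is less than 40 mg/kg. If the analyst enters 40 as the dose, exposure from a smaller dose is credited to a larger one.

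The error has a fixed direction. It pulls down the highest dose level, which has the most influence on the upper end of the slope, and so imitates less-than-proportional exposure. The level-based wording and the mg/kg labels could lead a programmer that way. Two competent programmers might then produce different slopes and different dose-normalised tables from the same data, which a SAP is meant to prevent.

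**Working it through.** The plan gives no figure on this point, so there is none to reproduce. The check asks where the cap binds, how large the error would be under the unfavourable reading, and which reading the text supports.

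**Inputs from the documents.** Levels 2.7, 8.0, 16.0, 26.7 and 40.0 mg/kg, six active participants each, cap 3000 mg (SAP 3.1). BMI 18 to 30 kg/m² and weight at least 50 kg (Protocol 5.1). Dosing by Day -1 weight (Protocol 6.1). Infused volume recorded (Protocol 6.4).

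**Where the cap binds.** Threshold weight = 3000/level.
- 40 mg/kg: 3000/40 = 75 kg, reachable within BMI 30 at any height above √(75/30) = 1.58 m.
- 26.7 mg/kg: 3000/26.7 = 112.4 kg, which needs √(112.4/30) = 1.94 m at BMI 30, so it is essentially never reached.
- 16 mg/kg: 3000/16 = 187.5 kg, out of reach; lower levels more so.

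Only cohort 5 matters. At 80 kg the actual dose is 3000/80 = 37.5 mg/kg (6.3% below nominal); at 90 kg it is 33.3 mg/kg (16.7% below).

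**Size in cohort 5 if nominal mg/kg were used.** Each participant's normalised value is multiplied by min(1, 75/W). The documents give no weight distribution, so this is an assumption: normal, mean 70 to 85 kg, SD 10 to 12 kg, truncated at 50 kg and at 97.2 kg (30 × 1.80²).

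| | Mean 70, SD 10 | Mean 85, SD 10 |
|---|---|---|
| Share above 75 kg | 31% | 82% |
| Chance that at least 1 of 6 active is capped | 90% | nearly 100% |
| Geometric mean of min(1, 75/W) | 0.976 | 0.898 |
| Bias in normalised exposure | -2.4% | -10.2% |

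The standard error of a six-person log-mean is √ln(1+CV²)/√6 = 0.081 at CV 20% and 0.120 at CV 30% (CVs assumed).

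**Size in the slope.** The log doses have mean 2.564 and sum of squared deviations 4.53. The top level deviates by 1.125, so its weight in the slope is 1.125/4.53 = 0.248.
- Low end: 0.248 × ln(0.976) = -0.006.
- High end: 0.248 × ln(0.898) = -0.027.
- Standard error: √ln(1+CV²)/√(6 × 4.53) = 0.038 (CV 20%) and 0.056 (CV 30%).

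With a looser upper weight limit of 110 kg and mean 85 kg, SD 12 kg, the cohort bias becomes -12.1% and the slope bias -0.032, still below one standard error.

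**Comparing the choices.** Simulated designs of five cohorts of six, with a true slope of 1 and clearance either independent of weight or proportional to it, gave these mean slopes:
- nominal mg/kg: 0.973 to 0.994;
- actual mg: 0.979 to 1.000, the low end arising only when clearance is proportional to weight;
- actual mg/kg: 0.998 to 1.000.

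**What the text supports.** V_z and V_ss are in litres, and V_ss is residence time multiplied by CL, so the dose in CL must be in mg, not mg/kg. Percent of dose recovered in urine makes sense only against the amount infused. A 90 kg participant nominally due 40 × 90 = 3600 mg but given 3000 mg would otherwise have recovery understated by one sixth. The word dose in this section therefore already means the amount given. The count of values per dose, the geometric means and the treatment labels need a grouping variable, and cohort supplies it; grouping does not fix the regressor or the divisor.

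**The case for a change.** The strongest opposing case is that a SAP should settle such choices before unblinding, that this error would be systematic, and that a sentence or two would remove it. At the heavier assumed weights the cohort 5 bias of 10.2% (0.108 on the log scale) exceeds one standard error of the cohort log-mean at CV 20% (0.081), and one heavy participant's normalised value could be 15% to 30% low. All of that stands as a description of the nominal reading.

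It does not stand as a description of the plan, because no sentence adopts that reading. Nor does asking for the amount actually given settle the matter: actual mg can still yield a slope near 0.98 when clearance is proportional to weight, not far from the nominal result. Choosing between mg and mg/kg is a judgement the pharmacokineticist can make with the data in view. The SAP's output shells, which set the content of tables and figures and may name the units, are not in the public text, so one cannot say that the point was left open everywhere.

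**Conclusion.** No change is needed. The observation is correct as far as it goes: the visible text of SAP 15.2 names neither the dose variable nor its unit, and the cap binds above 75 kg at 40 mg/kg. The plan nevertheless leads an analyst to a sound result. The section's other uses of dose require the amount given, and that amount can be derived from recorded volume and weight.

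Even under the unfavourable reading the effect is small: about 2% to 10% in one cohort's normalised exposure and 0.006 to 0.027 in the slope, below one standard error. These sizes rest on the assumed weights and CVs of 20% to 30%, and on a 40 mg/kg cohort being dosed. Protocol 4.1 plans up to five cohorts, and Protocol 6.5 lets the levels change.

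No decision depends on it. Protocol 9.1 tests no hypothesis, Protocol 9.3.2.1 treats proportionality as exploratory, and no interval or criterion is set for b. The 40 mg/kg level is the last one planned, so no planned escalation step follows it. Individual PK parameters and study treatment administration are both listed, so a reader can compare normalised exposure with CL and see who was capped. Naming the unit in the output would be good practice and can be done when the tables are programmed.
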